### 5.2 Electrocardiogram (ECG) and echocardiography (Echo)

Any signs of conduction disorders (bundle branch block / atrio-ventricular heart block) as well as biventricular hypertrophy in the ECG can be a sign of cardiomyopathy, which has been described under the medication with HCQ. In this case further cardiologic workup is necessary. If there are any signs or symptoms of cardiomyopathy the medication with HCQ must be discontinued immediately. (Fachinformation Quensyl® 2017) The Echo is done to assess for pulmonary hypertension and to exclude cardiomyopathy at the beginning of the study.

### 5.3 Check for Hypoglycemia

Any signs of hypoglycaemia like low blood glucose levels or reports of potential hypoglycaemic episodes will lead to intensified observation of blood glucose levels and if persistent change of medication (e.g. reduction or stop).

## 6 TRIAL METHODS

### 6.1 Assessment of efficacy

The primary outcome of the trial is the oxygen saturation, measured in room air. As the numbers of subjects that will be included into the trial will be low and cannot precisely be predicted, a spectrum of secondary outcome parameters will be interpreted exploratory, including patient oriented measures and outcomes, like quality of life.

## 7 Safety

### 7.1 Definitions

#### Adverse Event (AE)

According to GCP, an adverse event (AE) is defined as any untoward medical occurrence in a subject treated with a pharmaceutical product and which does not necessarily have a causal relationship with this treatment. An AE can be any unfavourable and unintended sign (including an abnormal laboratory finding), symptom, or disease temporally associated with the use of a medicinal (investigational) product, whether or not related to the medicinal (investigational) product.

An AE may be:

- a new symptom or a new diagnosis
- a new medical condition or an accident
- a change in laboratory parameters
- an intercurrent illness or accident
- worsening of a medical condition/diseases existing before the start of the clinical trial
- recurrence of a disease
- an increase in frequency or intensity of episodic diseases.

Surgical procedures themselves are not AEs; they are therapeutic measures for conditions that require surgery. The condition for which the surgery is required may be an AE. Planned surgical measures permitted by the clinical trial protocol and the condition(s) leading to these measures are not AEs, if the condition leading to the measure was present before inclusion in the trial. In the latter case the condition should be reported as medical history.

Change in laboratory parameters: The criteria for determining whether an abnormal test finding should be reported as an adverse event are as follows:

- Test result is associated with accompanying symptoms, and/ or
- Test result requires additional diagnostic testing or medical/ surgical intervention, and/ or
- Test result leads to a change in trial dosing outside of protocol-stipulated dose adjustments, or discontinuation from the trial, significant additional concomitant drug treatment, or other therapy, and/ or
- Test result is considered to be an adverse event by the investigator or sponsor.
- Progression of child under treatment should not be reported as an adverse event. However, if child leads to a fatal outcome during the trial or within the safety reporting period, then disease progression should be reported as an adverse event and as a serious adverse event with outcome “death”.

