The additional burden put on the children from participation in the study is minimal. Except for a sample for HCQ blood level measurements, no investigations or tests are performed which would not be performed outside the study setting, including ophthalmological investigation (Chapter 5.1), liver function tests, ECG testing (Chapter 5.2). Special thresholds cannot be given as they are heavily dependent on the initial condition and co-morbidities of the child. Any significant deviation from baseline (usually  $> 2$  fold upper limit of normal) will be reported as adverse event. These data are monitored systematically according to the protocol (Chapter 7) and the infants and children are very closely monitored by their physicians who decide withdrawal from the study depending on the condition of the subject.

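### Protocol 1.4 and 7.1 give unreconciled rules for when an abnormal laboratory value becomes an adverse event, so AE counts of asymptomatic elevations on which nobody acts may differ between sites.

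*Protocol*

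**What the plan says.** Protocol 1.4 (risk-benefit assessment) names eye examination, liver function tests and ECG, and then states a reporting rule. It begins with a qualifier: "Special thresholds cannot be given as they are heavily dependent on the initial condition and co-morbidities of the child". The next sentence opens "Any significant deviation from baseline", gives more than 2 times ULN as the usual guide, and closes "fold upper limit of normal) will be reported as adverse event". The text then refers the reader to Chapter 7 for how these data are monitored.

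Protocol 7.1 (Adverse Event, change in laboratory parameters) states its own rule: "The criteria for determining whether an abnormal test finding should be reported as an adverse event are as follows". Four criteria joined by and/or follow:

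- the finding comes with symptoms
- in the protocol's words, "Test result requires additional diagnostic testing or medical/ surgical intervention, and/ or"
- trial dosing is altered beyond the adjustments that the protocol provides for, the subject stops the trial, or significant treatment is added
- the investigator or the sponsor considers the result an AE.

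A last bullet concerns disease progression, not laboratory values. Section 7.1 contains no multiple of ULN and does not refer back to 1.4.

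On analysis, Protocol 8.4 and SAP 6.7.2.1 tabulate AEs as recorded. SAP 6.7.2.2 plans per-subject laboratory listings and summaries over time with exploratory p-values. Protocol 8.5 also plans shift tables from a normal baseline to outside the reference range. The SAP does not carry these over.

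**The concern.** Safety of HCQ is a secondary objective in both blocks. Protocol 4.1.1.3 lists liver damage, muscle disease and blood disorders among the known side effects, and 3.6.3 gives raised liver values as an example of a severe side effect that may lead to withdrawal. Such changes can appear first as a laboratory value without symptoms, and this is the situation in which the two sections give different answers.

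Up to 100 sites are planned. A site that follows 1.4 would normally record such a value as an AE. A site that follows only the list in 7.1 need not. The AE frequency tables would then pool counts made under two reporting rules. No planned SAP output would correct for this, because none counts, by arm, the subjects who exceed a stated limit.

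**Working it through.** The plan gives no figure to reproduce. The check sets the two rules side by side and then asks where a difference would show in the analysis.

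**Step 1. Where the rules diverge.** Take a value above twice ULN.

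| What happens with the value | Protocol 1.4 | Protocol 7.1 |
|---|---|---|
| Symptoms accompany it | normally an AE | AE |
| No symptoms, but extra testing or an intervention is required | normally an AE | AE |
| No symptoms, but a dosing change outside the protocol's own adjustments, discontinuation or significant added treatment follows | normally an AE | AE |
| None of these, but the investigator or sponsor judges it an AE | normally an AE | AE |
| None of these, and nobody judges it an AE | normally an AE | not required |

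Only the last row differs. It is not an empty category. The full panel is already scheduled again at START Visits 3 and 4 and STOP Visits 3, 4 and 5, so a site may wait for the next planned sample without ordering any additional test.

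**Step 2. What one such subject weighs.** Inputs: 80 subjects (Protocol 3.2 and 8.1), equal split between blocks expected (3.2), 1:1 allocation (3.5.1).

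- Subjects per arm within a block: 80 / 2 / 2 = 20.
- One subject counted under one rule and not the other: 1 / 20 = 5 percentage points in the row for that event. In the row for any AE, the proportion moves only if the subject has no other AE.

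How many such subjects to expect cannot be computed. The documents give no rate of laboratory elevations and no rate at which sites retest or act on them.

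**Step 3. Which laboratory data can compare the arms.**

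- START: post-baseline panels at Visits 3 and 4. The placebo group switches to HCQ after Visit 3, so only Visit 3 compares HCQ with placebo.
- STOP: full panels at Visits 3, 4 and 5, all within the blinded period. From Visit 6 only the drug level is measured. The contrast here is continued against withdrawn HCQ.

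**Step 4. What survives if the AE is not recorded.** The value remains in the listing and in the summaries over time. A mean or median over about 20 subjects can hide one or two large rises. The shift tables would show some of them, but they are in Protocol 8.5 only.

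**The case against.** The strongest reply is that the two sections can be followed together. Any one criterion in 7.1 is enough, and the last leaves the decision to the investigator or sponsor. A site can read 1.4 as guidance on how to use that discretion, and 1.4 itself points to Chapter 7. On this reading the fault is a missing cross-reference. Much of this stands: the rules are compatible, and a value that requires further testing is already an AE under 7.1. But 7.1 permits reporting the remaining case and does not require it, so sites may still handle it differently.

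A second reply is that laboratory safety is analysed independently of AE reporting. This also stands, and it limits the point to AE counts. A reader might infer that silent HCQ toxicity would go unseen. The documents do not support that, because every laboratory measure is listed per subject and summarised by treatment group.

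A reader might also take 2 times ULN as a firm cut-off that 7.1 contradicts. Section 1.4 declines to set fixed thresholds and qualifies both the deviation and the figure, so it too relies on judgement. A multiple of ULN also does not fit ECG or eye findings, or low blood counts.

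Finally, recruitment began in Q4 2015, and the SAP already comments on how few patients were in both blocks. A change to 7.1 may come too late for most subjects. That is a fair limit on the protocol part of the remedy, but not on the SAP part.

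**Conclusion.** The inconsistency is real and narrow. Protocol 1.4 and 7.1 state different rules, neither is given precedence, and the SAP does not settle the matter. The consequence is that AE counts of asymptomatic elevations on which nobody acts may vary with the section a site follows.

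The size is 5 percentage points of an arm per affected subject. This assumes the planned 80 subjects, equal blocks and 1:1 allocation; with fewer subjects each one weighs more. The number affected is unknown. It is also assumed that AE frequency tables are produced as in SAP 6.7.2.1, although the opening of SAP section 6 suggests listings only.

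A reader might infer that the HCQ-placebo difference in AEs is pulled towards zero by a known amount. If a share f of these cases were reported in both arms, the difference for them would be f × (p1 − p0), where p1 and p0 are the true proportions in the HCQ and placebo arms. The documents give none of these three quantities, so no amount can be stated.

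**What to change.** **Protocol.** Reconcile the two passages so that one rule for abnormal laboratory findings stands in 7.1, and let 1.4 refer to it. Which rule to adopt is for the sponsor to decide. Cost: one line. It helps only subjects who have not yet completed. If it is made during the trial, the date of the change should be recorded, because AE reporting before and after it may differ.

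**SAP 6.7.2.2.** Two additions, taken directly from the laboratory values and so independent of how sites reported:

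1. Restore the shift tables of Protocol 8.5.
2. Add a count, by arm, of subjects exceeding the guide value already named in 1.4 (2 times ULN), for parameters where an upper limit is meaningful. Show subjects already above it at baseline separately. For the between-arm comparison, use Visit 3 in START and Visits 3 to 5 in STOP. Report START Visit 4 descriptively.

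The guide value serves here to summarise data and does not by itself define an AE. Cost: one or two derived tables and no new data, provided that the laboratories' reference limits are on file, as Protocol 8.5 presupposes.

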### 3.4 Secondary outcome parameters

For both, **START** and **STOP** HCQ blocks absolute and relative change under the active compound from trial day 1 (i.e. Visit 2), to START block: day 28 (i.e. Visit 3), STOP block: day 84 (i.e. Visit 5) each, will be compared to change under placebo. The following variables will be investigated:

Oxygen saturation ( $O_2$ -sat, in room air) (only absolute, as relative already primary outcome)  
 Respiratory rate (RR, in room air) (relative and absolute)

Retractions (yes/no)  
 Coughing (yes/no)  
 Oxygen demand

$pO_2$ ,  $pCO_2$  (capillary, in room air)

Chest x-ray

Quality-of-life

Health economics

Overall survival

Weight for height

Cumulative amounts of steroid equivalents. Clinical course of lung disease (since last visit):  
 Healthy/ Sick-better/ Sick-same/ Sick-worse/ Patient died

Pulmonary exacerbation (since last visit)

If  $> 5$  years old (If a child  $\leq 5$  years is already able to perform the listed investigations (spirometry or bodyplethysmography), these should also be performed and documented at the discretion of the investigator.)

The following lung function parameters will be assessed:

FEV1 % predicted (recorded in L), FEV 1 (L), FVC % predicted (recorded in L), FVC (L); MEF 75 (L/s); MEF 50 (L/s); MEF 25 (L/s); TLC (L); ITGV (L); RV (L); R eff (kPa\*s/L); R eff predicted (%).

→ reference values according to the GLI 2012 lung function regression equations

6 minute walking distance (meter)

$O_2$ -saturation before and after 6MWT

Borg scale

If ventilated:

Duration (h) of mechanical ventilation

NO (%), ECMO yes/no, if yes VA/VV, double lumen vs. single lumen, Flow-rate.

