### 7.5 Immediate reporting of SAEs by investigator

SAEs must immediately (within 24 hours of the investigator's awareness) be reported to:

**IZKS Mainz  
[name]  
[name]  
[contact]**

The initial SAE Report should be as complete as possible including the essential details of subject's identification (screening number, random number), the serious adverse event (medical term, diagnosis), the trial medication and the assessment of the causal relationship between the event and the trial medication. The SAE report must be reviewed and signed by the investigator. The investigator should provide related additional information on the clinical course and the outcome of each SAE as soon as possible (Follow up report). The "Serious Adverse Event Form" will be provided.

Worsening of a sign or symptom of the condition under treatment will normally be measured by efficacy parameters. However, if the outcome fulfils the definition of "serious adverse event", it must be reported as such.

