6.7.1 Efficacy

For both, START and STOP HCQ blocks absolute and relative change under the active compound from trial day 1, i.e. Visit 2, to START block: day 28, day 56 STOP block: day 84 each, will be compared between treatment groups .

The following variables will be investigated:

- Oxygen saturation (O2-sat, in room air) (only absolute, as relative already primary outcome)
- Respiratory rate (RR, in room air) (relative and absolute)
- Retractions (yes/no)
- Coughing last 24 h (yes/no)
- Oxygen requirement (yes/no)
- pO2, pCO2 (capillary, in room air)
- Chest x-ray scoring for chILD
- Overall survival (time from randomization until death; if no death observed, time will be censored at time point of last (follow-up-)visit): a Kaplan-Meier plot will be provided; if possible, the median overall survival and corresponding 95%-confidence interval will be calculated
- Cumulative amounts of steroid equivalents per time period
- If > 5 y old
 - FEV1 % predicted (recorded in L)

- FVC % predicted (recorded in L)
- reference values according to the GLI 2012 lung function regression equations
- 6 minutes walking distance (meter)
- O2-saturation before and after 6MWT
- If ventilated:
 - Duration (h) of mechanical ventilation
 - NO (%), ECMO yes/no, if yes VA/VV, double lumen vs. single lumen, Flow-rate.

Additionally, FEV₁, FVC, FVC predicted, 6 min walking distance will be displayed by Box-Plots and All-in-one plots over each time point.

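### Protocol 7.1 and 7.5 conflict on reporting serious non-fatal progression, and no planned SAP table counts patients whose lung disease worsened by a defined criterion

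*Protocol*

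**What the plan says.** **Reporting rules.** Among the things that may be an AE, Protocol 7.1 lists "worsening of a medical condition/diseases existing before the start of the clinical trial". At the end of the bullets on laboratory findings, the same section adds: "Progression of child under treatment should not be reported as an adverse event". The exception is disease that "leads to a fatal outcome during the trial or within the safety reporting period", which is then both an AE and an SAE. The seriousness criteria in 7.1 include life-threatening events and hospitalisation as well as death. Footnote 2 to those criteria says that the hospitalisation criterion is not met when an admission is unconnected with an adverse event, and gives a social admission as its example.

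Protocol 7.5 says: "Worsening of a sign or symptom of the condition under treatment will normally be measured by efficacy parameters". It continues that if the outcome fulfils the SAE definition, "it must be reported as such".

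**Outcomes and analyses.** Protocol 3.4 names pulmonary exacerbation and clinical course of lung disease as secondary outcomes for both blocks. Clinical course has the categories "Healthy/ Sick-better/ Sick-same/ Sick-worse/ Patient died". Tables 1-1 and 1-2 schedule both at every visit and phone contact, and the exacerbation form asks whether the patient was hospitalised.

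SAP 6.7.1 introduces its efficacy list with "The following variables will be investigated". Neither outcome is in that list, in the variable list of SAP 4.2.1, or in the SAP schedules. SAP 4.2.2 says only that symptoms and clinical course of treatment will be documented. The responder table in SAP 6.6 has a single definition, improvement, for START and STOP alike.

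**The concern.** In the STOP block the harm to look for is deterioration after HCQ is replaced by placebo. Such deterioration can be recorded as a safety event or as an efficacy outcome, and the plan is weak on both routes. On the safety side, whether an admission for progression becomes an SAE depends on which section the site follows. On the efficacy side, to which 7.5 sends ordinary worsening, the SAP omits the two outcomes that record worsening most directly and does not carry over the worsening-based withdrawal responder.

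At stake are the consistency of SAE reporting across up to 100 planned sites (Protocol 3.2) and a plain answer to how many patients got worse in each arm. Protocol 1.2 names a risk and benefit decision among the aims, and Protocol 1.4 calls the risk of giving placebo acceptable. A count of patients who worsened bears directly on both.

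**Working it through.** No figure in the plan needs reproducing, so the check compares the passages.

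**Step 1: what each section requires, by type of progression**

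| Progression of chILD | Protocol 7.1 | Protocol 7.5 | Consistent? |
|---|---|---|---|
| Not serious | Not an AE under the specific sentence | Left to efficacy parameters | Yes |
| Serious, not fatal | Not an AE; the exception covers death only | SAE | No |
| Fatal | AE and SAE | SAE | Yes |

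The conflict is confined to the middle row. Footnote 2 in 7.1 adds to it. A site that takes progression not to be an AE can take an admission for progression to be unconnected with an AE, and so outside the hospitalisation criterion. A site that follows 7.5 would report the same admission within 24 hours. The position of the progression sentence, among the laboratory-finding criteria, also leaves its scope unclear.

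**Step 2: do the planned efficacy outputs capture the worsening that 7.5 sends to them?**

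- Pulmonary exacerbation is in Protocol 3.4 and Tables 1-1 and 1-2. It is absent from the SAP schedules and from SAP 4.2.1 and 6.7.1.
- Clinical course, with its Sick-worse category, is in the same protocol places. The SAP says it is documented and plans no analysis.
- The STOP responder in Protocol Tab 3.8-1 is defined by a saturation decrease of at least 5%, a respiratory rate increase of at least 20%, or newly needed support, with corresponding rules for high-flow and ventilated patients. In SAP 6.6 it is a saturation increase of at least 5%, or a decrease of at least 20% in flow or oxygenation index, or support no longer needed, for both blocks.

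**Step 3: what can still show worsening under the SAP**

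- SAP 6.7.1 compares changes from day 1 to day 84 between STOP arms for saturation, respiratory rate, retractions, cough, oxygen requirement, blood gases, chest x-ray score, FEV1, FVC, walking distance and ventilation. It also analyses survival.
- SAP 6.1 tabulates reasons for premature discontinuation.
- SAP 6.7.2.1 counts SAEs, deaths and AEs leading to discontinuation. SAP section 6 says that AE data will be listed only, so these two places also need reconciling.

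**Step 4: limits of those outputs.** A change from day 1 to day 84 misses an exacerbation that has resolved by day 84. SAP 5.1 substitutes no missing values, so a patient who worsens and leaves without a day-84 measurement contributes no change score; Protocol 3.6.3 lists life-threatening aggravation as a withdrawal reason. The yes/no items could show patients newly needing oxygen, but no shift table is specified. Survival apart, the day 85 to 168 observation period has no planned efficacy comparison.

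**Step 5: scale.** With 80 patients, an equal split between blocks (Protocol 3.2) and 1:1 allocation, STOP would have 80 / 2 / 2 = 20 per arm. One patient is then 1/20 = 5 percentage points of an arm, so a few admissions reported differently would visibly change a by-arm SAE comparison.

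**The case against.** The strongest reply has four parts.

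First, 7.5 can be read as an explicit override: worsening is an efficacy matter until it is serious, and then it is reported. The AE list in 7.1 is permissive, and a general list followed by a specific exclusion is not in itself a contradiction. This stands for non-serious worsening. It does not settle the serious non-fatal case, because 7.1 states its own exception, limits it to death, and does not refer to 7.5.

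Second, keeping an efficacy outcome out of AE counts is a legitimate design choice, especially where worsening is itself the primary outcome of the withdrawal block. That is a fair argument for the protocol. It is weaker for the SAP, which no longer defines the STOP responder by worsening.

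Third, secondary outcomes are exploratory, and Protocol section 8 allows the SAP to modify the plan, with deviations justified in the final report. This stands and limits the seriousness of the omission. The SAP gives no reason for it, however, and the data are collected.

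Fourth, SAP 6.6 writes in the past tense that there were too few patients in both blocks. This suggests that enrolment was known when the SAP was written, so a protocol clarification may come too late to change reports already made. The fix therefore includes a check of existing records.

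A reader might go further and infer that harm from HCQ withdrawal would appear in no planned output at all. The documents do not support that. The outputs in step 3 can all show deterioration, the SAE counts among them if sites follow 7.5. What is missing is a direct count.

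**Conclusion.** The point holds in two limited parts. The protocol gives conflicting instructions for serious non-fatal progression, and footnote 2 in 7.1 makes under-reporting by a site that follows 7.1 plausible. The SAP omits two protocol secondary outcomes and the worsening-based withdrawal responder, so no planned table counts patients whose lung disease worsened by a defined criterion.

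The size cannot be stated as a number of events, because neither document gives a rate of progression, exacerbation or admission. The 5 points per patient in step 5 rest on the planned numbers and the expected equal split, not on actual enrolment. That sites will in fact report differently is a risk inferred from the wording; nothing in the documents shows that it happened. This should be put right, but it does not undermine the trial's exploratory purpose.

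**What to change.** 1. Reconcile the progression sentence in Protocol 7.1 and footnote 2 on admissions with 7.5, so that one SAE reporting rule applies to serious non-fatal progression, and state whether the sentence applies beyond laboratory findings.
2. Where sites have already reported, compare exacerbation records marked as hospitalised with the SAE listing and query the mismatches. Not every mismatch is an error, since 7.1 also exempts pre-planned admissions and stays under 12 hours.
3. In SAP 6.7.1, add by-arm counts of patients with at least one pulmonary exacerbation, and of patients with clinical course Sick-worse or Patient died. Use START Visit 2 to 3, the placebo-controlled period, and STOP Visit 2 to 5, with STOP days 85 to 168 shown separately. Counting over all contacts keeps patients who leave early in the table up to their last contact.
4. Reconcile SAP 6.6 with the withdrawal column of Protocol Tab 3.8-1. The counts in item 3 do not depend on this.

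The reporting and table changes cost one short protocol clarification and one extra exploratory table from data already collected, plus a limited record check. No treatment rule changes.
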